Appendix 4 EQ5D Index Score

The EQ5D consists of the EQ5D descriptive system and the EQ VAS. The descriptive system is made up of 5 dimensions: mobility, self-care, usual activities, pain/discomfort and anxiety/depression. Each dimension has 3 levels: no problems, some problems, extreme problems (see scoring algorithm below). A unique health state is defined by combining 1 level from each of the 5 dimensions. There are 243 possible health states defined on this way. Each state is referred to in terms of a 5 digit code. Any missing values which are coded as '9' will be set to missing (and hence no health state value will be calculated). Ambiguous values (e.g., 2 boxes ticked for a single dimension) should be treated as missing values. If 1 or more domains are missing the health state value (HSV) will not be calculated.

For example, if a subject provides the following responses: Mobility=No problems, Self-care=No problems, Usual Activities=Some problems, Pain/Discomfort=Moderate problems, Anxiety/Depression=Extreme problems, his response sequence is 11223. The 243 theoretical possible sequences can then be mapped to a HSV to provide a summary across all dimensions. The tariff to be used for the mapping is that given by Dolan (1997). The scoring algorithm is as follows (the value set for UK is used in calculating EQ5D on this study):

Full health (11111)	1.000
Constant term (for any dysfunctional state)	-0.081
Mobility level 1	0
Mobility level 2	-0.069
Mobility level 3	-0.314
Self-care level 1	0
Self-care level 2	-0.104
Self-care level 3	-0.214
Usual activities level 1	0
Usual activities level 2	-0.036
Usual activities level 3	-0.094
Pain/discomfort level 1	0
Pain/discomfort level 2	-0.123
Pain/discomfort level 3	-0.386
Anxiety/depression level 1	0
Anxiety/depression level 4	-0.071
Anxiety/depression level 3	-0.236
At least one domain at 3 (N3)	-0.269

The HSV for the subject with example sequence 11223 = 0.255, calculated as follows:

- 1) Full health =1
- 2) Minus constant: -0.081
- 3) Minus mobility level 1: 0
- 4) Minus self-care level 1: 0
- 5) Minus usual activities level 2: -0.036
- 6) Minus pain/discomfort level 2: -0.123
- 7) Minus anxiety/depression level 3: -0.236
- 8) Minus N3: -0.269

Where level 1 corresponds to no problems, level 2 to some problems, and level 3 to extreme problems.

Reference

Dolan P. Modeling valuations for EuroQol health states. Med Care, 1997; 35(11):1095-108.

Appendix 5 Protocol deviations

A list of major PDs that could potentially impact efficacy analysis and may exclude a subject from PP population is as follows:

- Study treatment administration errors
- Eligibility criteria not met
- Disallowed/prohibited concomitant therapies
Note: The programming produces a draft list of potential prohibited medications based on ATC codes for the medical/clinician review on an ongoing basis; a final list of protocol deviations (includes prohibited medications) is determined before the database lock after a joint team review and included into the relevant dataset.
- EASI assessment was not performed at week 24 visit as per the protocol
- Blinding has been compromised
- Did not sign ICF at all
- Other reasons, as outlined in the most recent version of the Protocol Deviation Specification document

Final determination of protocol deviations as major or minor will occur during blinded review prior to the unblinding of the study.

Appendix 6 Intrinsic or extrinsic AD

Classification of intrinsic or extrinsic AD will be based on IgE and/or eosinophil counts and will be defined after reviewing the overall data before DBL.

Appendix 7 Validation of the NRS responder analysis

To assess the appropriateness of responder thresholds in the NRS responder analysis (an improvement of weekly average pruritus peak NRS ≥ 4), an approach combines an anchor-based approach and ROC curves will be performed to identify the responder thresholds that best predict classification based on an external criterion. First, an external anchor or another external criterion that is appropriate to identify responders (e.g., Pruritus PCS) is used to classify all subjects into responder (at least 1 grade improvement from baseline in PCS) or non-responder groups. Then, to check for appropriateness, the relationship between the PCS criterion and the NRS measure (change from baseline in weekly average pruritus peak NRS) is examined through correlation analyses. Finally, the predictive accuracy of how well the specific NRS change scores relate to the classifications is evaluated using logistic regression analyses and graphically displayed as an ROC curve. Each point on the curve provides the sensitivity (true positives) versus one minus the specificity (false positives) trade-off for identifying responders for a specific unit of change on the NRS measure. The entire range of change scores and the likelihood classifications are provided within the one curve. A diagonal line is included in the figure as a reference. Evaluations that produce curves close to the diagonal line should be viewed with caution because the diagonal line represents chance classification.

The area under curve (AUC) and its 95% CI will be presented, along with percent concordant and discordant.

The analyses described above will be performed using all data across all visits and the data at week 24.

The following cumulative distribution function (CDF) plots will be produced to illustrate the between treatment group differences and within-subject change from baseline to Week 24.

- CDF plot illustrating the treatment differences from baseline to Week 24
- CDF plot of peak pruritus change score from baseline to Week 24 for all subjects by the different PCS response options at Week 24
- CDF plot of peak pruritus change score from baseline to Week 24 for all subjects by the PCS change scores (differences) between baseline and Week 24 (e.g. ± 3 , ± 2 , ± 1 , and 0 point change)

In addition, the mean change in peak pruritus NRS from baseline to Week 24 will be calculated in the following subjects:

- An improvement of ≥ 1 in PCS from baseline to week 24
- 50-74%, 75-89%, or 90-100% improvement in EASI from baseline to week 24
- An improvement of ≥ 2 in IGA scale from baseline to Week 24
- An IGA of 0 or 1 at Week 24

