5 SELECTION AND DISPOSITION OF CLINICAL TRIAL POPULATION

5.1 Number of subjects

Approximately 250 subjects will be screened to result in 200 randomized subjects (50 subjects per group).

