4.2 General Presentation Considerations

Unless otherwise stated, descriptive summaries will be presented by treatment group. In all tables the treatment groups will be presented in the order of Placebo, Nemolizumab 10 mg, Nemolizumab 30 mg, and Nemolizumab 90 mg. Comparisons on the difference between each nemolizumab group and placebo will be presented.

Continuous data will be summarized in terms of the mean, standard deviation (SD), median, minimum, maximum, lower quartile (Q1), upper quartile (Q3), and number of observations, unless otherwise stated. Where data are collected over time, both the observed data and change from baseline will be summarized at each time point. The minimum and maximum will be reported to the same number of decimal places as the raw data recorded in the database. The mean, median, Q1, and Q3 will be reported to one more decimal place than the raw data recorded in the database. The SD will be reported to 2 more decimal places than the raw data recorded in the database. In general, the maximum number of decimal places reported shall be four for any summary statistic.

Categorical data will be summarized in terms of the number of subjects providing data at the relevant time point (n), frequency counts and percentages. Percentages will be presented to one decimal place. A percentage of 100% will be reported as 100%. Percentages will not be presented for zero counts. Percentages will be calculated using n as the denominator. If sample sizes are small, the data displays will show the percentages, but any textual report will describe

frequencies only. Changes from baseline in categorical data will be summarized using shift tables where appropriate.

P-values greater than or equal to 0.001, in general, will be presented to three decimal places. However, if a p-value is only presented to four decimal places (by SAS) it will not be rounded again, but will be presented to four decimal places. P-values less than 0.001 will be presented as “<0.001”, and p-values greater than 0.999 will be presented as “>0.999”.

Confidence intervals (CIs) will be presented to one more decimal place than the raw data.

All report outputs will be produced using SAS® version 9.3 or a later version in a secure and validated environment. The outputs will be provided as individual TLFs in RTF format and all TLFs in one PDF bundle.

All statistical tests will be two-sided and will be performed at the 5% level of significance, unless otherwise stated.

Baseline

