‘Baseline’ is defined as the last available assessment prior to the first administration of study drug, if it exists; otherwise, ‘baseline’ is defined as the last available assessment prior to date of randomization.

For diary data (pruritus NRS, PCS, Sleep disturbance NRS), the baseline values will be derived from data collected during the 7 days prior to the first administration of study drug. Baseline score will be the weekly prorated average of non-missing subject diary scores reported during the 7 days. A minimum of 4 daily scores out of the 7 days is required to calculate the weekly prorated average score.

Analysis Visit

Study day is relative to date of randomization. Day -1 is the day before randomization, and day 1 is date of randomization.

Assessments at early termination and unscheduled visits will be slotted based on the following visit window.

Period	Analysis Visit	Target day (relative to randomization)	Day ranges
Run-in	Screen	<1	<1
Treatment	Baseline	1	≤1
	Week 1	8	2-11
	Week 2	15	12-22
	Week 4	29	23-43
	Week 8	57	44-71
	Week 12	85	72-99
	Week 16	113	100-127

	Week 20	141	128-155
	Week 24	169	156-183
Follow-up	Week 28	197	184-211
	Week 32	225	>211

The diary reported during study will be classified into analysis visits as follows (i.e., during the 7 days prior to the target day of analysis visit. In this case, the target day of analysis visit is relative to date of the first administration of study drug.):

- Day -7 to -1 = Baseline
- Day 1 to 7 = Week 1
- Day 8 to 14 = Week 2
- Day 22 to 28 = Week 4
- Day 50 to 56 = Week 8
- Day 78 to 84 = Week 12
- Day 106 to 112 = Week 16
- Day 134 to 140 = Week 20
- Day 162 to 168 = Week 24
- Day 190 to 196 = Week 28
- Day 218 to 224 = Week 32

These analysis visits will be used in the calculations for all week-based parameters collected on subject's diary (e.g., pruritus NRS, PCS, Sleep disturbance NRS). Other non-diary data, such as EASI, IGA, BSA, SCORAD, DPS, DLQI, HADS, EQ5D, 5-D itch, missed work/school day, vital signs, body weight, clinical laboratory assessments, respiratory assessment/PEF, will be analyzed according to actual scheduled visits.

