4.7.2 Primary Efficacy Endpoint

The primary variable for the assessment of efficacy is the percent change from baseline in EASI at week 24.

The primary endpoint will be analyzed using a MMRM approach, including terms of treatment group, and baseline IGA severity for ITT and PP populations. Visit will be fitted as a categorical variable, with the effect of treatment group and baseline IGA varying at each visit (i.e., interaction between treatment group and visit and interaction between baseline IGA and visit). The corresponding baseline values of the response variable will be included as a covariate in the model. An unstructured (UN) covariance matrix for repeated measures within a subject will be used to model the within-subject errors in the analysis, unless there are issues related to convergence. If the UN covariance matrix leads to non-convergence, then Akaike's information criterion (AIC) will be used to select the best covariance matrix among autoregressive, compound symmetric, and Toeplitz. The Kenward-Rogers adjustment will be used with restricted maximum likelihood (REML) to make proper statistical inferences. Denominator degrees of freedom will be estimated using approximation of Kenward-Rogers. A linear contrast will be used, within the MMRM framework, to estimate difference between each nemolizumab

dose regimen and placebo. LSmeans with 95% CI and the corresponding statistical p-value will be presented for the treatment difference between each nemolizumab dosing regimen and placebo at a given visit.

Other covariates may be explored and will be added into the model, if appropriate.

Dose Response Analysis: MCP-Mod approach will be applied using a set of candidate dose-response models (see table below) to test for a dose-response relationship via model-associated statistics. The analysis will be performed using the available R software package “MCPMod” or any other available software.

Linear	E _{max}	Sigmoid E _{max}
Linear	1. ED50=10mg 2. ED50=30mg	1. ED50=10mg, H (Hill)=1 2. ED50=10mg, H (Hill)=2 3. ED50=10mg, H (Hill)=3 4. ED50=15mg, H (Hill)=2 5. ED50=20mg, H (Hill)=4 6. ED50=30mg, H (Hill)=2

ED50=dose produces 50% of maximum effect

Sensitivity analysis: The robustness of the primary analysis will be investigated by performing the sensitivity analyses as described in 4.7.1.3.

Subgroup analysis: The homogeneity of the treatment effect for a number of important subgroups will be investigated as described in 4.7.1.6.

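### SAP Appendix 7 pools all visits for the NRS ROC analysis but makes no provision for repeated records from one subject in the pooled AUC confidence interval

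*SAP*

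**What the plan says.** Appendix 7 of the SAP sets out how the 4-point responder threshold on weekly average peak pruritus NRS will be checked. The suggested anchor is the PCS, "used to classify all subjects into responder (at least 1 grade improvement from baseline in PCS) or non-responder groups". The ability of the NRS change score to predict that classification "is evaluated using logistic regression analyses and graphically displayed as an ROC curve". The reported result is described as follows: "The area under curve (AUC) and its 95% CI will be presented, along with percent concordant and discordant".

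The same appendix then defines two data sets for this work: "The analyses described above will be performed using all data across all visits and the data at week 24". It does not list the pooled visits, say how the interval is computed, or mention a subject effect, a clustered variance or resampling by subject.

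SAP Section 4.2 maps diary days to post-baseline weeks 1, 2, 4, 8, 12, 16, 20 and 24, and continues through follow-up to "Day 218 to 224 = Week 32". Elsewhere the SAP deals with repeated measures explicitly. For the primary endpoint (Section 4.7.2), "An unstructured (UN) covariance matrix for repeated measures within a subject will be used to model the within-subject errors in the analysis", and Section 4.7.3.4 applies the same model to change in peak NRS.

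**The concern.** An ordinary logistic regression and its AUC interval treat each row as a separate, independent observation. In the pooled data set the rows come in groups of up to 8 or 10 from one person. Positive correlation within those groups is likely: every change score for a subject subtracts the same baseline, the week 1 and week 2 diary windows are adjacent, and subjects stay in the same treatment group throughout. The pooled data then carry less information than the row count suggests, and an interval that ignores this is too short.

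What is at stake is how the validation reads. The pooled and week 24 results are listed side by side with no order of priority. A pooled interval that looks much tighter than the week 24 one invites more reliance on it than it has earned.

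**Working it through.** The documents state no AUC, interval width or within-subject correlation, so there is no figure of the plan's own to reproduce. The check is a simulation of what an independent-records interval would do.

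**Inputs from the documents**
- Subjects: 200 randomized (Protocol Section 5.1).
- Post-baseline diary visits: 8 to week 24, or 10 with weeks 28 and 32 (SAP Section 4.2).
- Records pooled, at most: 200 × 8 = 1,600 or 200 × 10 = 2,000.

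**Assumed inputs (not in the documents)**
- AUC about 0.84.
- The same within-subject correlation (ICC) for NRS change and for the latent scale behind the PCS response: 0, 0.3, 0.5 or 0.7.
- Correlation 0.7 between the two measures, both for the subject effects and within visits, and a mean response that rises over the visits.

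**Formulas**
- AUC = share of responder/non-responder record pairs in which the responder record has the larger NRS improvement.
- Independent-records variance (DeLong) = S10/m + S01/n, with m responder and n non-responder records.
- Clustered variance (Obuchowski) = S10/m + S01/n + 2·S11/(mn), with the components summed within subject before they are squared or multiplied.
- Coverage = share of 800 replicates in which the estimate lies within 1.96 SE of the mean AUC.

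**Results** (ratio = empirical SE / independent-records SE, taken before rounding)

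| Visits | ICC | Independent SE | Empirical SE | Ratio | Coverage, independent | Coverage, clustered |
|---|---|---|---|---|---|---|
| 8 | 0 | 0.0096 | 0.0095 | 0.99 | 95.0% | 94.8% |
| 8 | 0.3 | 0.0096 | 0.0105 | 1.10 | 93.6% | 95.2% |
| 8 | 0.5 | 0.0096 | 0.0125 | 1.30 | 87.2% | 94.6% |
| 8 | 0.7 | 0.0096 | 0.0156 | 1.62 | 77.1% | 93.1% |
| 10 | 0 | 0.0086 | 0.0088 | 1.03 | 94.5% | 94.6% |
| 10 | 0.3 | 0.0086 | 0.0102 | 1.18 | 91.1% | 93.9% |
| 10 | 0.5 | 0.0086 | 0.0119 | 1.38 | 84.5% | 94.5% |
| 10 | 0.7 | 0.0086 | 0.0150 | 1.74 | 73.9% | 94.8% |

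Simulation error in a coverage figure is √(0.95 × 0.05 / 800) = 0.8 percentage points near 95% and √(0.74 × 0.26 / 800) = 1.6 points near 74%. The loss at ICC 0.3 with 8 visits (1.4 points) is therefore within about twice the simulation error; the losses at 0.5 and 0.7 are not.

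**Half-widths at ICC 0.5, 8 visits**
- Independent records: 1.96 × 0.0096 = 0.019.
- Clustered: 1.96 × 0.0125 = 0.025.
- Week 24 alone (one record per subject, SE about 0.029): 1.96 × 0.029 = 0.057.

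The naive pooled interval looks 0.057 / 0.019 = 3.0 times as precise as week 24. The clustered one is 0.057 / 0.025 = 2.3 times as precise.

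**Sensitivity**
- 25% dropout (assumed), ICC 0.5, 8 visits: ratio 1.28, coverage 87.5%.
- Correlation unequal between the two measures or present in only one (0.6 against 0 or 0.1; AUC about 0.76 to 0.78): ratio 1.09 to 1.25, coverage 88.1% to 92.1%.
- A separate set of simulations (8 visits, 2,000 trials per setting, AUC about 0.83) gave ratios of 1.15, 1.40 and 1.68 and coverage of 91%, 83% and 74% at 0.3, 0.5 and 0.7. The direction agrees; the exact size depends on how the data are generated.
- Week 24 alone, in the eight settings of the table: coverage 93.2% to 94.8% with no correction.

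**The case against.** The strongest reply is that the SAP names no method for the interval. A reader might infer that it prescribes an analysis that ignores repeated measures. It does not: the text is silent, and a careful programmer could cluster by subject without departing from it. That limits the point to an unaddressed issue. It does not remove it, because the procedure described is a plain logistic regression with concordance percentages. Run literally, that treats rows as independent, whereas the efficacy sections of the same SAP spell out the within-subject covariance.

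A reader might also infer that the precision of the 4-point threshold would be overstated, and that the responder endpoint is therefore in doubt. The documents do not support this. An AUC interval describes discrimination over all cut-points, and no interval for the cut-point is planned. The threshold is fixed in advance in Protocol Section 7.1.2.2, and Section 7.6 cites a minimum clinically important difference of 3 to 4. Protocol Section 9.1.5.2.2 presents the ROC work as further validation. No decision rule uses the interval; the only caution in Appendix 7 is about curves near the diagonal. With an AUC near 0.84, half-widths of 0.019 and 0.025 both stay far from 0.5.

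Finally, the companion week 24 analysis has one record per subject, so clustering does not arise there. The cumulative distribution plots and the anchor-group mean changes in Appendix 7 are also for week 24. All of this stands, and it keeps the point small.

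**Conclusion.** The point holds as a minor one. Appendix 7 plans a pooled-visit AUC interval without providing for repeated records from the same subject. With an independent-records method that interval would be too narrow under positive within-subject correlation. For an assumed ICC of 0.3 to 0.7 and an AUC of about 0.84, the true SE is roughly 1.1 to 1.7 times the naive SE, and actual coverage of the nominal 95% interval is about 94% to 74%. At zero correlation there is no narrowing.

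The omission is plain in the text, and the direction follows from positive correlation. The size is illustrative: it rests on the assumed ICC, AUC and number of pooled visits, and on an independent-records method being used. The pooled AUC estimate, the week 24 interval, the pre-set threshold, the CMH test on the responder endpoint, the primary analysis and the sample size do not change.

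**What to change.** Add to Appendix 7, for the pooled analysis:

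- which visits are included, in particular whether weeks 28 and 32 are;
- that the 95% CI for the AUC comes from a bootstrap that resamples whole subjects, or from a clustered-data AUC variance such as Obuchowski's. The latter gave 93.1% to 95.2% coverage in the settings tabulated above.

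Naming the week 24 analysis as the main one would also settle which interval readers should rely on.

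Refitting the logistic model by GEE is not a substitute. With NRS change as the only predictor, the AUC depends only on the ranking of the change scores. GEE alters the standard error of the coefficient and leaves the AUC interval as it was.

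The cost is a sentence or two in the SAP, a few lines of code and a wider reported interval. No new data are needed.

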Appendix 8 Potentially clinically significant values (PCSV) for clinical laboratory tests

Parameter	SI Units	Conventional Units	PCSV
			<3.0 Giga/L & ≥3.0G/L at Baseline (non-Black)
WBC	x10e9/L	x10e3/μL	<2.0 Giga/L & ≥2.0G/L at Baseline (Black) : ≥16.0 G/L & <16G/L at Baseline :
Neutrophils ABS	x10e9/L	x10e3/μL	<1.5 Giga/L & ≥1.5G/L at Baseline (non-Black) <1.0 Giga/L & ≥1.0G/L at Baseline (Black)
Eosinophils ABS	x10e9/L	x10e3/μL	(>0.5 Giga/L and >ULN) and (≤0.5 Giga/L or ≤ULN at Baseline)
Basophils ABS	??	??	>0.1 Giga/L and ≤0.1 Giga/L at Baseline
Monocytes ABS	??	??	>0.7 Giga/L and ≤0.7 Giga/L at Baseline
Lymphocytes ABS	x10e9/L	x10e3/μL	>4.0 Giga/L and ≤4.0 Giga/L at Baseline <0.5 Giga/L and ≥0.5 Giga/L at baseline ≤100 g/L and Baseline >100 g/L for Male ;
Hemoglobin *Female *Male	g/L	g/dL	≤ 90 g/L and Baseline >90 g/L for Female ≥200 g/L and baseline <200 g/L for Male; ≥180 g/L and Baseline <180 g/L for Female
Platelets	x10e9/L	x10e3/μL	<100 Giga/L and ≥100G/L at Baseline ≥700 G/L & <700G/L at Baseline ≤130mmol/L and Baseline >130
Sodium	mmol/L	mmol/L	: ≥155 mmol/L and Baseline <155 <3mmol/L and Baseline ≥3
Potassium	mmol/L	mmol/L	>6.0 mmol/L and Baseline ≤6.0

Parameter	SI Units	Conventional Units	PCSV
Calcium (Total)			<7 mg/dL and Baseline ≥7 mg/dL
Corrected serum calcium	mmol/L	mg/dL	>12.5 mg/dL and Baseline ≤12.5 mg/dL
Glucose	mmol/L	mg/dL	<2.2mmol/L and ≥2.2 mmol/L at Baseline >13.9mmol/L and ≤13.9mmol/L at Baseline
Creatinine	µmol/L	mg/dL	≥150µmol/L (Adults) and Baseline <150µmol/L
AST	U/L		>3 ULN and Baseline ≤3 ULN
ALT	U/L		>3 ULN and baseline ≤3 ULN
Alkaline phosphatase	U/L		>2.5 ULN and Baseline ≤2.5 ULN
Bilirubin total	µmol/L	mg/dL	>2.0 ULN and Baseline ≤2.0 ULN
CPK	U/L		: >3.0 ULN and Baseline ≤3.0 ULN
Fibrinogen	g/L	mg/dL	Not provided
GGT	U/L		>2.5 ULN and Baseline ≤2.5 ULN
Albumin	g/L	g/dL	≤30 g/L and Baseline >30g/L
Uric acid			>600 µmol/L and ≤600 µmol/L at Baseline for Male;
*Male16-59			>500 µmol/L and ≤500 µmol/L at Baseline for Female
*Female>16	mmol/L	mg/dL	
*Male >60			
Cholesterol total	mmol/L	mg/dL	>10.34 mmol/L and ≤10.34 mmol/L at Baseline
Triglycerides	mmol/L	mg/dL	>5.7 mmol/L and ≤5.7 mmol/L at Baseline

CCI

Electronic Signature Page

This page is the manifestation of the electronic signature(s) used in compliance with CCI CCI electronic signature policies and procedures and in compliance with applicable regulations.

UserName: PPD
Title: Senior Statistical Programmer, CCI
